The design is an 8-week randomized, double-blind, placebo-controlled trial, with an 8-week open-label extension, of Daily Essential Nutrients (DEN; Hardy Nutritionals), and a 30-, 60-, and 365-day follow-up phone call or in person-visit. The follow-up calls will also assess for safety following study completion. Parent/guardian and child ratings, using standardized measures, will evaluate adherence, side effects and AEs (Aim 1); ADHD-associated mood and irritability (Aim 2); and ADHD symptoms (Aim 3), thus allowing evaluation for clinical significance. Other domains of psychopathology will be evaluated for purposes of sample characterization and secondary analyses. The design consists of three study periods, which are individualized for each participant as they enroll:

Child RCT Protocol 2017

1. Screening and baseline. Participants will be screened by phone through a conversation with the parent/guardian for study eligibility. Those who are eligible and consent/assent to the study will receive a baseline assessment (see below for definition of eligibility and assessment).
2. An 8-week period of fully randomized, placebo-controlled, treatment.
3. An 8-week open-label extension period (OL).

Study data collection will occur in-person at baseline and at weeks 4, 8, 12, and 16 and via phone 30-60- days after end-of-open label and 365- days after enrollment. Details of data collection are outlined in Tables 1 & 2 located on the last two pages of this proposal.

Study Population

Number of subjects

Sample size power calculations are based on using power = 0.8, with a two-tailed $\alpha=0.05$, and the a priori decision to detect a medium effect size ($d \geq .5$) with a primary parent-rated measure that is a combination of CASI-5 subscale scores. Given the three sites and two treatments; a 3:2 randomization ratio, active-to-placebo; and assuming two dropouts per arm, per site, based on a previous study (Rucklidge, 2017), ($n = 12$ total), sample needed to recruit = at least 135, with at least 123 retained. To account for the 3 sites and the 3:2 randomization, a number divisible by 15 is needed, so, $n = 45$ participants per site.

In terms of feasibility, we estimate being able to recruit the required number of participants over a period of 12-18 months, given proven success in recruitment for a vitamin D supplementation trial ([name]) and established success recruiting participants in a longitudinal study on ADHD ([name]).

Inclusion Criteria

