At the two US sites, the child participant will be paid \$10 per in-person assessment (n=5), in the form of a gift card, (see Table 1 for assessment schedule) for a total of \$50. Gift card payment will be made for each instance the child completes the questionnaires and measures associated with that assessment time point. If the child declines to answer any questions, questionnaires and measures despite reassurance or assistance including by parent and the study coordinator, or actively declines to participate at any visit, s/he will be discontinued from the study. Children will also be paid \$10 for each blood sample provided, and \$5 for each of the other biological samples they provide, for up to \$105 for each of the 3 time points. Except for blood, children will not be withdrawn from the study for not providing a biological sample (hair, saliva, stool, urine), but the samples collection will be prioritized as part of the study. Parent/guardians will be paid \$20 for traveling to the site for in-person assessments, for a total of 5 visits during the main, 16 weeks of the study (\$100), and additionally, \$10 for questionnaires completed online and over the phone at 2-month follow up, or \$20 for parents and \$10 for the child, if 2-month follow up occurs in person. One year after enrollment in the study, participant families will be contacted regarding their willingness to provide follow-up data including questionnaires and, potentially, biological samples. Parents and children will be paid for that in-person visit, or phone visit, according to the previously described schedule: \$10 for phone completion; \$20 to parent for in-person completion; \$10 to child for in-person completion; \$5 for each biological sample provided, except blood, \$10.

At the Canadian site, payment to participants is not expected or customary. As such, parents will be given \$25 gift vouchers for their participation in the qualitative part of the study (i.e. in-person interviews) and will be reimbursed for cost of travel, including parking and mileage per onsite visit. In Canada, blood and urine will not be collected due to storage limitations. Health Canada, the Canadian equivalent of the FDA, has not required collection of blood.

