Once consent and assent are given, the parent/guardian and child will complete the other baseline questionnaires electronically, also via the REDCap web portal. Details regarding the measures are noted in the section below (starting on page 13). Participant will also have weight, height and blood pressure measures taken and recorded electronically in the REDCap portal. Any paper-collected ratings data will be entered weekly.

Child RCT Protocol 2017

Blood, hair, saliva, and urine samples will also be collected from the child participant at the baseline assessment, along with the stool sample, if possible. If the child cannot give a stool sample at the baseline visit, the parent will be given the collection kit and instructed to collect the sample later that day or the next morning, before the child begins taking the capsules. The samples will be stored as below, in order to examine nutrient levels, systemic inflammation, DNA methylation, metabolomics and microbiome markers. Except for the blood sample at baseline and week 8, the child will not be excluded from the study without providing any one, or all, of the biological samples (hair, saliva, urine or feces). Child-appropriate information sheets will be provided to the participants to explain the biological sample collection and receipt of parent/guardian consent and child assent will be documented. Aside from blood, which will be collected and stored per laboratory requirements, samples that are collected will be entered on a paper study sample log, by site (A1 A=Oregon, sample 1, saliva; etc), along with the participants ID number. For stool and hair, a record of the serial number of the collection container will be added to participant's REDCap record. Hair and urine collection will be noted in participants' REDCap record.

Blood pressure, heart rate, height and weight will also be assessed at in-person visits by a trained research assistant using instruments calibrated according to hospital maintenance schedule. Participants will be asked to complete the VioScreen version of the Food Frequency Questionnaire (FFQ) at baseline and at the end of eight weeks with input from one parent/guardian.

Enrollment

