Participant safety is the most important consideration. Participants may be discontinued from the study if they show adverse symptoms of either a physical or psychological nature in response to the treatment. Evidence of significant or poorly tolerated side-effects will stop a participant's participation in the study, in the judgement of the PI and in consultation with the study physicians. Mandatory stop concerns will include: possible or probable allergic reaction, new onset of severe and persistent suicidal ideation deemed related to study product, or emergence of exclusion criteria. If a participant's psychological state deteriorates to a clinically significant degree during the trial, the investigator will discuss with the participant and parent/guardians the possibility of withdrawing from the study, or may decide that the participant should be withdrawn. Participants or their parent/guardian may request to be withdrawn from the study or withdraw consent at any time without penalty. If a participant, for any reason, requires treatment with certain therapeutic agents (i.e. antibiotics), we will note what they are taking and for how long. If a protocol exclusion violation has occurred (i.e. participant requires psychiatric medications), his or her involvement will be discontinued, but they will be followed for the duration initially anticipated for descriptive purposes. If any patient is discontinued from the trial, we will carry out follow-ups and appropriate referrals for treatment linkage, to ensure participant well-being.

Human subjects' protection

Child RCT Protocol 2017

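### No week-8 parent rating is required after the study itself stops a child, and one group's follow-up is labelled descriptive despite the intention-to-treat analysis

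*Combined protocol and SAP*

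**What the plan says.** **Stops decided by the study.** Risk assessment and right to withdraw states: "Evidence of significant or poorly tolerated side-effects will stop" the child's participation in the study, on the investigator's judgement with the study physicians. The same section lets the investigator withdraw a child whose psychological state worsens to a clinically significant degree. It also ends involvement after an exclusion violation, such as a need for psychiatric medication, and says of those children: "they will be followed for the duration initially anticipated for descriptive purposes". It closes by promising follow-ups and referral for any discontinued patient, for the child's well-being. Human subjects' protection returns to exclusion violations and gives well-being as the purpose of follow-up.

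**Refusal by the child.** The payment paragraph under Setting and Recruitment methods says of a child who will not answer questions: "or actively declines to participate at any visit, s/he will be discontinued from the study".

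**Voluntary withdrawal.** The Data Safety Monitoring Plan asks for permission to keep questionnaire follow-ups so that the intention-to-treat analysis is preserved. The sentence is attached to families who choose to withdraw.

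**Analysis.** Number of subjects describes "a primary parent-rated measure that is a combination of CASI-5 subscale scores". Data Analysis names the CASI-5 subscales and the clinician CGI as primary, includes all randomised children in the group assigned, and applies LOCF to those who do not complete 8 weeks.

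**The concern.** The plan does not separate stopping the study product from stopping data collection. The primary rating comes from the parent, so it can often be obtained after the child has stopped. Nothing in the text seen asks for it after a study-initiated stop, and for exclusion violators the word descriptive leaves open whether a week-8 score belongs in the main analysis. Two analysts could handle the same child differently.

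Side-effects, deterioration and the start of other treatment may all be related to symptoms, so the missing values may be informative. LOCF would then put a value from before the event in place of the week-8 outcome. Unlike an analysis choice, a rating that was never sought cannot be recovered later.

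**Working it through.** **1. What happens after each route out**

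| Route | What the plan provides afterwards | Outcome measure named? |
|---|---|---|
| Side-effects | Follow-up and referral, for well-being | No |
| Deterioration, investigator withdraws | The same | No |
| Exclusion violation | Full planned duration, as descriptive (Risk assessment); well-being (Human subjects' protection) | No |
| Child declines measures or a visit | Not stated; possibly handled as withdrawn assent | No |
| Family withdraws | Permission sought to keep questionnaires for intention-to-treat | Questionnaires, in general |

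Only the last row is tied to the intention-to-treat analysis.

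**2. Which value would be carried forward**

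- *Parent CASI-5.* Table 1 schedules it at baseline, week 4 and week 8, so week 4 is normally carried. The measures table after Table 1 lists the wider set of subscales only at baseline and at the ends of the two phases, with the targeted ones monthly. For any subscale outside the targeted set, or a stop before week 4, baseline would be carried.
- *CGI.* It is scheduled at baseline, week 8 and week 16. If the severity scale is meant, baseline is carried. The documents do not say which CGI scale is primary, and an improvement scale has no baseline value. The CGI-Improvement ratings in the dosing section serve dose decisions and do not appear in Table 1.

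**3. The plan's own loss figure**

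Number of subjects works by "assuming two dropouts per arm, per site": 2 × 2 arms × 3 sites = 12, and 135 − 12 = 123. Both figures reproduce. At 3:2, 135 splits into 81 active and 54 placebo, so the losses are 6/81 = 7.4% and 6/54 = 11.1%, a gap of 3.7 points. This gap comes from equal counts in unequal arms and does not predict an imbalance. The 12 cover all causes; the number of study-initiated stops is not given.

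**4. Size with no true effect**

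Shift = gap in loss rate × change missed. Assumptions: both arms improve by 0.3 to 0.5 SD; children lost would have reached their arm's mean; half the change is present by week 4.

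| Losses (active v placebo) | Gap | Baseline carried | Week 4 carried |
|---|---|---|---|
| 6 v 6 (all 12) | 0.0370 | 0.011–0.019 SD | 0.006–0.009 SD |
| 3 v 3 (half study-initiated, assumed) | 0.0185 | 0.006–0.009 SD | 0.003–0.005 SD |
| 5% v 20% (assumed) | 0.15 | 0.045–0.075 SD | 0.023–0.038 SD |

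Example: 0.0370 × 0.3 = 0.011 and 0.0370 × 0.5 = 0.019. Under these assumptions the shift favours the arm with the lower loss rate.

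For scale, the standard error of the standardised difference before baseline adjustment is √(1/81 + 1/54) = 0.176. The range 0.003 to 0.019 is about 2% to 11% of that.

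**5. Size with a true difference of 0.5 SD and all 12 losses**

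- Baseline carried: 0.8 × 0.926 − 0.3 × 0.889 = 0.474; 1.0 × 0.926 − 0.5 × 0.889 = 0.481.
- Week 4 carried: 0.8 × 0.963 − 0.3 × 0.944 = 0.487; 1.0 × 0.963 − 0.5 × 0.944 = 0.491.

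**The case against.** **Much is already covered.** Follow-up is promised for any discontinued patient, exclusion violators are followed for the full duration, and Data Analysis includes everyone randomised and uses the final assessment. If a week-8 rating exists, it would normally be that assessment. This stands, and it narrows the point: the rating may not be sought, or may be set aside as descriptive. A reader might infer that discontinued children are simply abandoned, or that exclusion violators' scores will be dropped. The documents say neither.

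**Refusal is withdrawn assent.** Consent and Assent tells the child that a change of mind is allowed, so the voluntary-withdrawal wording may apply. That is a fair reading, though not a stated one. The refusal rule also sits in a paragraph that begins "At the two US sites, the child participant will be paid"; read literally it covers 90 of the 135 planned children (2 × 45). It is therefore not the main ground here.

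**Blood refusal.** A reader might add this as a further route, from "Except for blood, children will not be withdrawn from the study for not providing a biological sample" and "Except for the blood sample at baseline and week 8, the child will not be excluded from the study". It has almost no content for this purpose. Willingness to give blood is an inclusion criterion, baseline sampling ordinarily precedes randomisation, Table 1 next schedules blood at week 8, when the parent rating is also due, and the Canadian site collects none.

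**Using scores after other treatment is an estimand choice.** This is true and not free. If 3 of 54 placebo children gained an extra 0.5 to 1.0 SD on medication (assumed), the contrast would move by 3/54 × 0.5 to 1.0 = 0.028 to 0.056 SD, more than the planned-loss shift above. The reply is that the plan already commits to intention-to-treat.

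**Limits of the text.** The consent pages and parts of the recruitment and cross-site coordination text were not seen; they may contain relevant contact rules.

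**Conclusion.** The point holds as a gap in data collection and an inconsistency in wording. After a stop for side-effects, deterioration or an exclusion violation, the text seen does not require the week-8 parent CASI-5. Labelling one group's follow-up descriptive conflicts with an analysis of all randomised children.

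A reader might infer a serious bias; the documents do not support that. At the planned losses the shift is about 0.003 to 0.019 SD, and a true 0.5 SD would be estimated at 0.474 to 0.491. These figures rest on the assumed improvement, on half the change being present by week 4, on lost children resembling their arm and, for the lowest values, on half of the losses being study-initiated. Baseline carry-forward for the CGI further assumes the severity scale. The effect grows only if losses are larger or more unequal, and the rate, balance and direction of study-initiated stops are unknown. The reason to act is that the remedy is cheap and makes the plan consistent with its own analysis.

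**What to change.** - Extend the questionnaire wording in the Data Safety Monitoring Plan to study-initiated discontinuation, and reconcile the payment paragraph, Risk assessment and right to withdraw, and Human subjects' protection with it.
- With parent permission, and within the consent and assent terms, seek the parent CASI-5 at the remaining scheduled time points of the randomised phase, including week 8. REDCap can be used if needed, as it already is at post-study follow-up. Seek the CGI where it can be rated, since it draws partly on the child's own report.
- State in Data Analysis that these ratings, including those after an exclusion violation, enter the intention-to-treat analysis, and that LOCF applies only where no week-8 rating was obtained. Replace the descriptive label accordingly.

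Decisions on stopping and on study product stay with the investigators.

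**Cost.** An amendment approved by the ethics board at each of the three sites, a check of consent and assent wording, and some contact effort with families who have stopped. The intention-to-treat estimate will include data after other treatment has started; the per-protocol analysis already planned serves as a comparison.

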Each site will submit an identical protocol to their internal IRB or ethics committee. All study protocols and materials (identical for each site, except where differentiation or specification is required by an individual IRB) will be approved by the IRB/ethics committee at that site. Details concerning coordination of activities are located in the Multi-Site Coordination section.

Phone screen

At initial phone contact, which will be initiated following contact from the potential participants, a study coordinator/research associate will conduct a phone screen with interested families by outlining the purpose of the study, confirming willingness to participate by asking eligibility questions from the inclusion and exclusion criteria below. Parent/guardians of females will be asked if they have begun menstruating. If yes, parent/guardian will be asked whether child is sexually active. If yes, or unsure, potential participant will need to take a urine test at baseline as a pregnancy screen. Any questions of the parent/guardian and potential participant will be answered as well. Parent will be asked for the email address of a teacher, coach, or other adult who knows the child, and CASI-5 questions will be sent to that person to answer on behalf of the child. The questionnaire will be sent to the teacher or named adult using the email provided, via the secure REDCap system.

Child RCT Protocol 2017

Only children who are ADHD-medication-free for at least 2 weeks prior to in-person assessment will be scheduled for an in-person screening assessment and considered for participation. A phone screen process has been used with success in multiple previous studies by one of the co-investigators [49] If the child is eligible based on the screening, the parent will be send the CASI-5 screening questions to their email via REDCap. The screening questions come from the ADHD and DMDD/ODD sections of the CASI-5 (see details of this process in the Baseline Assessment section below).

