Phone screen data, including inclusion/exclusion criteria, and the CASI-5 responses will be reviewed and discussed by the study PIs and the research assistant. Any questions or concerns regarding enrollment, based on information provided by the parent/guardian or participant, may be handled with phone or in-person consultation with an onsite study physician. If necessary, the consultation or meeting enables a brief review of medical history and the opportunity to identify any potential concerns prior to enrollment.

Consent and Assent

After eligibility is established based on phone screen and CASI-5 responses, and review of medical records and/or site physician assessment, if necessary, the parent/guardian and child will be invited to meet with a research staff team member for a baseline visit, in designated office space at one of the three sites to discuss the study and to complete consent and assent prior to any study procedures. Prior to the first visit, the consent and assent forms will be sent to the parent/guardian for review in before the first meeting. This will facilitate the parent's ability to formulate and ask questions in advance of the first visit. The consent will be signed onsite, using REDCap.

As this study represents minimal risk to the child and offers potential benefit, the consent of one parent/guardian will be sufficient for participation. The child will be provided with information about the study using simple language that is appropriate for a child as young as 6 years of age. The child will be clearly told that s/he does not have to participate, s/he can change his/her mind at a later time. Provided that both the parent/guardian and child want to participate, both will provide electronic consent/assent via the secure, HIPAA-compliant REDCap web portal. Documentation of assent/consent, via an electronic signature, will be captured for each participant and parent/guardian. If the parent/guardian or child does not consent/assent or is excluded for any other reason, data already collected will be retained for the purpose of characterizing those who made contact. The reason for not enrolling will be noted in REDCap. Parents will be asked whether they are interested in communicating regarding the MADDY research study via text. A separate consent form will be provided and the text communication explained.

Procedures

Baseline Assessment

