3. **Child Target Problem-** At baseline, child will be asked to nominate his or her biggest problem or symptom. If the child cannot select just one, two may be named. The research assistant and child discuss the named problem and the RA asks questions about the frequency, duration and interference level of the problem. The example field allows for the construction of a brief narrative of the behavior and its impact on family life. The target symptoms are reviewed and the narratives revised at subsequent visits. A panel of four judges, blind to treatment condition, will independently review the narratives to rate change from baseline on a 9-point scale: 1, normal; 2, markedly improved; 3, definitely improved; 4, equivocally improved; 5, no change; 6, possibly worse; 7, definitely worse; 8, markedly worse; 9, disastrously worse. The mean of the four raters will be compared with primary and key secondary ratings from the original study.
4. **Treatment Acceptability**– upon study completion, the child participant will be asked for their opinion on participation and any suggestions they have to improve the study, and whether they would recommend the trial to others with symptoms.

In person at the end of the RCT

5. **Child assessment of the blind** will be captured by asking the youth whether they believe they are taking the placebo or real product.

Teacher or Other Adult-rated measures

Completed at baseline and 8 week RCT, 16-week end-of-study – time: 10 minutes:

1. **CASI-5** selected subscales (3 eligibility subscales and peer relationships) will used at baseline and to monitor the effectiveness of the child’s response to intervention at two other time points.

Data and Specimens

Blood, hair, saliva, urine, and feces collection

Collected at baseline, 8 weeks and week 16 (end-of-study) – time: 5-10 minutes

Blood collection

Per FDA requirements, participants will be **required** to provide blood samples at each in-person visit. These samples will be used for safety measures and for research purposes. Analysis will include CBC, TSH, iron, a number of supplemented nutrients including B vitamins and Vit D, and

Child RCT Protocol 2017

blood for future analysis of targeted and untargeted metabolomics and IL-6 and TNF-a. Total blood collection will be approximately 18ml, or 3 teaspoons. See “Blood Sample Collection Info for OHSU” chart included in IRB submission, for details.

Hair Collection

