One risk for participants, if they were taking stimulant medication that conferred a benefit in terms of ADHD symptoms, is that by coming off the medication, their symptoms may return. Risks to participants in terms of taking the micronutrients are low, but as with any intervention there are potential side effects. These may include transient gastrointestinal upset (loose stool, nausea), and headache, particularly if product is taken on an empty stomach. If these side effects are experienced and believe to be related to taking the micronutrients, these symptoms should go away if pills are taken with food and water as directed, and tend to lessen after a day or two of taking the pills, or when participant ceases taking the pills. Not all participants will receive the active treatment in the first 8-weeks, but everyone will have the opportunity to knowingly take the active treatment in the second 8-week, open-label phase. In terms of specific personal benefit, some participants may find that taking the micronutrients help with the symptoms of ADHD and irritability, as well as aggressive behavior. However, participants may or may not personally benefit from being in this study.

The product to be studied has the largest amount of published research in the mental health field for a complex micronutrient product. Data were examined from all known published and unpublished

Child RCT Protocol 2017

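### The teacher CASI-5 that serves as baseline is sent, undated, during the phone screen, so some children may be rated on medication at baseline and off it afterwards

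*Combined protocol and SAP*

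**What the plan says.** **When the teacher form goes out.** The Phone screen section describes the initial phone contact. Within it, "Parent will be asked for the email address of a teacher, coach, or other adult who knows the child", and the "CASI-5 questions will be sent to that person to answer on behalf of the child". Neither sentence is dated. The same section later adds: "Only children who are ADHD-medication-free for at least 2 weeks prior to in-person assessment will be scheduled".

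**What the teacher form is for.** Under Teacher or Other Adult-rated measures, the CASI-5 is "Completed at baseline and 8 week RCT, 16-week end-of-study". The selected subscales are described as "3 eligibility subscales and peer relationships) will used at baseline and to monitor the effectiveness" of the response at two later times. Table 1 marks the teacher row at baseline, week 8 and week 16 and not at the phone screen. The measures table after Table 1 gives the form 10 minutes. No second pre-treatment teacher form is described.

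**When medication must have stopped.** The Inclusion Criteria and the Phone screen section count the two weeks back from the in-person assessment. Exclusion 5 names the in-person assessment in one clause and the screening in the next.

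**How change is analysed.** Data Analysis compares change from baseline between randomized groups by ANCOVA with baseline as covariate. Enrollment places randomization after consent and the baseline questionnaires.

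**The concern.** Read as written, the only pre-treatment teacher mailing belongs to the phone screen, and its answers become the baseline for the teacher outcome. Because the medication-free period is counted back from the in-person visit, it may begin after that call. A child still taking ADHD medication when the teacher answers would have a medicated baseline and unmedicated scores at weeks 8 and 16. The Risk/benefit analysis section recognises that "by coming off the medication, their symptoms may return".

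Two things are at stake. Change within each arm would combine stopping medication with the study treatment. This matters most at week 16, where everyone has been offered active product and there is no control group. The baseline would also predict the week-8 score less well, which costs precision in the planned ANCOVA. Sites could time the form differently as well, since no window is given.

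**Working it through.** **1. Timing.** The protocol states no figure on this point, so the check begins with the order of events.

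- Phone contact: teacher's email requested and CASI-5 sent (Phone screen).
- Eligibility settled from the phone screen and CASI-5 responses, before the baseline visit (Consent and Assent).
- Medication-free period complete by the in-person visit (Inclusion Criteria, Phone screen).
- Consent, baseline questionnaires, enrollment, randomization (Consent and Assent, Baseline Assessment, Enrollment).
- Teacher form again at weeks 8 and 16 (Teacher or Other Adult-rated measures, Table 1).

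Nothing places the teacher's answer after the medication-free period. The post-consent steps under Baseline Assessment mention only parent and child questionnaires.

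**2. Inputs for size.** These are assumptions, since the documents give no values:

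- share on medication when the teacher answers, f = 0.2 to 0.5;
- medication effect on the teacher score, s = 0.5 to 1.0 SD;
- correlation of unmedicated baseline with week 8, r = 0.5 to 0.7.

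The unmedicated score has SD 1. Medication lowers the score by s in a fraction f of children, unrelated to their unmedicated score.

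**3. Formulas.**

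- Observed baseline variance: V = 1 + f(1 − f)s².
- Observed correlation: r_obs = r / √V.
- Ratio of ANCOVA residual variances: (1 − r_obs²) / (1 − r²).
- Ratio of confidence-interval widths: square root of that ratio.
- Shift in within-arm change: + f × s, toward worsening, in both arms.

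**4. Results.**

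| f | s | r | V | r_obs² | Variance ratio | CI ratio | Within-arm shift |
|---|---|---|---|---|---|---|---|
| 0.2 | 0.5 | 0.5 | 1.04 | 0.240 | 1.013 | 1.006 | +0.10 SD |
| 0.3 | 1.0 | 0.6 | 1.21 | 0.298 | 1.098 | 1.048 | +0.30 SD |
| 0.5 | 1.0 | 0.7 | 1.25 | 0.392 | 1.192 | 1.092 | +0.50 SD |

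In the middle row r_obs falls from 0.60 to √0.298 = 0.545.

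**5. Check on bias.** A simulation used 123 children at 3:2 (the retained number under Number of subjects), r = 0.6 and a true effect of −0.5 SD.

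| f | s | Change, active | Change, placebo | ANCOVA difference | Power |
|---|---|---|---|---|---|
| 0 | – | −0.50 | 0.00 | −0.50 | 0.92 |
| 0.3 | 0.5 | −0.35 | +0.15 | −0.50 | 0.92 |
| 0.3 | 1.0 | −0.20 | +0.30 | −0.50 | 0.90 |
| 0.5 | 1.0 | 0.00 | +0.50 | −0.50 | 0.89 |

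The arm difference is unchanged throughout. In the last row a true improvement in the active arm disappears from its within-arm change, while power falls only from 0.92 to 0.89.

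**The case against.** **The timing is inferred.** The Phone screen section gives no sending or completion date, and the explicit schedule puts the teacher form at baseline. An early form has a natural screening use: the inclusion criteria require symptoms in more than one setting, and the teacher items are called eligibility subscales. Table 1's phone-screen row for CASI-5 eligibility questions names no rater, so it could cover an early teacher form. This stands as far as it goes: the text permits an on-medication baseline but does not establish one. Against it, one teacher form is described as both baseline and comparator for two later times, with no separate screening version.

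**Washout may come first.** Exclusion 5's reference to screening could mean the phone screen, which Design Overview describes as screening by phone. It could equally mean the in-person visit, which the Phone screen section calls a screening assessment. So it cannot be said that washout is timed only to the in-person visit. The two reference points need reconciling.

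**Bias.** A reader might infer that the week-8 treatment effect is confounded with washout. It is not. Medication status at the teacher's rating is fixed before randomization and balanced in expectation, as the simulation shows.

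**Consent.** A reader might infer that sending the form breaches the rule "to discuss the study and to complete consent and assent prior to any study procedures". The documents do not support that. The same section settles eligibility from the phone screen and CASI-5 responses before the consent visit, so it does not count screening among those procedures. Consent pages and some other text were also removed from the copy reviewed, and authority for early screening could lie there.

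**Importance.** Hypotheses 2 and 3 name parent, child and clinician ratings, and the sample size rests on a parent-rated measure. That stands, although Data Analysis lists the CASI-5 subscales as primary without naming the rater.

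**Conclusion.** The point holds as a minor improvement to a supporting outcome. The protocol attaches an undated teacher mailing to the phone screen and treats the same form as the outcome baseline, so an on-medication baseline is possible for some children.

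The randomized week-8 contrast remains unbiased. Over the assumed ranges, residual variance is 1–19% higher, the confidence interval about 0.6–9% wider, and within-arm change 0.10–0.50 SD closer to worsening. The last matters only if within-arm change is reported, which is the natural summary at week 16; the planned analysis in Data Analysis is between groups.

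All of this depends on how many children are still medicated when the teacher answers, which the documents do not say. If every child has already met the medication-free period by then, the effect is nil and only the wording needs repair.

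**What to change.** - Reconcile Exclusion criteria, Phone screen, Teacher or Other Adult-rated measures and Table 1 on the reference point for the medication-free period and on the timing of the teacher form.
- At the phone screen, collect the teacher's email. If a teacher rating is needed then for the multi-setting eligibility check, label it a screening form and show it in the phone-screen column of Table 1.
- Send, or repeat, the outcome-baseline teacher form once the protocol's medication-free period has been met and before the first capsule. State the window in Table 1.
- Specify that score as the covariate in the teacher ANCOVA and as the reference for teacher change at weeks 8 and 16.

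The cost is a changed REDCap sending date, or at most one repeat of a 10-minute form. Some teacher forms may come back late.
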